3 MEASUREMENT DEVICES

[figure not shown]
[figure not shown]
Device 1: VICORDER®

Device		
 Company: SMT Medical Model: VICORDER®: Arterial Stiffness Model Location: Wurzburg, Germany Oscillometric cuffs inflate at sub-systolic pressures to detect changes in the pressure waveform. Different sized cuffs are available.
Example Set-up		
 The cuffs can be placed on any 2 arterial segments. In the figure to the left, pressure cuffs placed over the brachial and femoral arteries. A small balloon is placed over the carotid artery to obtain a measurement for cfPWV. A low pressure (50 mmHg) is used for this site with minimal discomfort.
Raw Data		
 Top display = pressure waveform from proximal arterial segment Bottom display = pressure waveform from distal arterial segment Intrinsic software automatically detects the foot of the waveform of each arterial segment
Data Analysis		
 A = Site of proximal artery B = Site of distal artery Pulse wave velocity (PWV) = distance (D) / transit time (TT) Straight line distance (L) = Distance between two cuffs as measured according to manufacturer guidelines

[figure not shown]
[figure not shown]
		
 Transit Time (ΔT or TT) = Time between foot of proximal and distal waveforms. Oscillometric pressure waveforms will be determined at the brachial artery of the non-dominant arm using the VICORDER® in order to determine brachial and central arterial blood pressures.
Data Reduction		
 L is plugged into software prior to measurement. TT is averaged across 3 waveforms, and used to calculate one PWV Process repeated 3 times, for 3 PWVs per measurement cycle. Closest 2 PWVs averaged and used as outcome for measurement cycle.

[figure not shown]
Device 2: Transcranial Doppler (TCD)

Device		
 Company: Compumedics DWL Model: Transcranial Doppler Sonography TCD Location: Charlotte NC, USA DiaMon headset can be adjusted in 3 ways to accommodate each individual Connection between rear band and side panel sits behind the ear, below the occipital bone to ensure signal TCD probes should be in contact with head if headset has been fitted correctly
Example Set-up		
 Ensure probe is positioned over the temporal window Apply ultrasound gel to probe and/ or temporal window Move probe until faint trace appears and then make further fine movements to increase trace of artery velocity

Raw Data		
 Signal quality is indicated by color: the more yellow, the stronger the signal Gain and depth adjust can be made in the signal window. Gain should sit between 38-44 for optimal signal output Typical velocities for middle cerebral artery (MCA) are ~80 cm/s-1, and ~60 cm/s-1 in older populations Typical depth for MCA is 45-55
Data Analysis		
 Using a custom macro, the software (Labchart) identifies the peak of the ECG R- wave and the peak of the second derivative of each pressure waveform (corresponds to foot), then calculate the transit time (TT) between said peaks. Pulse wave velocity (PWV) = distance (L) / TT
Data Reduction		
 Measures of brain PWV, MCA velocity, static CA and neurovascular coupling will be collected from this device are continuously recorded during a testing session Data reduction for this protocol will require the selection of 30s epochs at specific time points to observe how PS and MS are impacting measures of CVH In the picture to the left, a researcher selected a time period to report the data collected during this time. A strict protocol will be followed to ensure that selection of 30s epochs are synchronized amongst all measures and research participants to prevent bias.

Device 3: Non-Invasive Blood Pressure (NIBP)

Device		
 Company: ADInstruments Model: Human NIBP Nano System, Finapress Location: Sydney, Australia Single cuff contains an infrared photoplethysmographic (940 mmHg) sensor and inflatable cuff. PPG sensor continuously captures the pulse waveform. Inflatable cuff used to calibrate waveform Height correction unit corrects for hydrostatic pressure changes due to change in hand position relative to the heart.
Example Set-up		
 Device placed between distal and proximal inter-phalangeal joint of the index finger. Wrist apparatus is strapped to the individual's non-dominant wrist
Raw Data		
 Data captured using a data acquisition system (PowerLab). Also displayed are electrocardiogram (ECG) signals captured by PowerLab.

[figure not shown]
[figure not shown]

- LabChart 8 can perform real time or offline function, including data averaging, peak detection, derivatives etc.

Data Reduction		
 • All measures collected from this device are continuously recorded during a testing session • Data reduction for this protocol will require the selection of 30s epochs at specific time points to observe how PS and MS are impacting measures of CVH • In the picture to the left, a researcher selected a time period to report the data collected during this time. • A strict protocol will be followed to ensure that selection of 30s epochs are similar amongst all measures and research participants to prevent bias.
-----------------------	--	---

Device 4: Doppler Ultrasound

[figure not shown]
[figure not shown]
[figure not shown]
Device		
 • Company: GE Healthcare • Model: Logiq P6 • Location: Chicago, IL • An 11L linear probe will be used for this protocol
---------------	--	---

Example Set-up		
 Measurement of blood flow through the carotid artery using a linear probe Probe is placed parallel to the blood vessel 10s videos of the common carotid, vertebral, and internal carotid arteries will be collected at each designated time point in the protocol Participants will be instructed to hold one's breath for the duration of the recording to ensure a clear video will be captured of the observed artery
Raw Data		
 Ultrasound videos are recorded at 30 Hz using an external video capture system Debut Professional (v4.0, NCH Software®) is used to record the present image on the Ultrasound device for later analysis Image to the left shows an example video captured by this software
Data Analysis		
 The captured videos will be analysed offline using specialized image analysis software (FMD Studio®,) shown to the left. The software measures and exports second-by-second diameters and blood velocities Cardiovascular Suite (Quipu, v3.5.3) analyzes raw ultrasound footage Coordination with ECG will produce measures of blood flow
Data Reduction		

[figure not shown]
- Lab-designed macro cleans raw data output generated by the video analysis software
- Macro is capable of calculating blood flow along with other measures that define the flow profile of the observed artery

[figure not shown]
[figure not shown]
[figure not shown]
Device 5: Continuous Wave Near-Infrared Spectroscopy with Spatially Resolved Spectroscopy (cwNIRS-SRS or NIRS)

Device		
 • Company: Artinis Medical Systems • Model: Portalite • Location: Amsterdam, Netherlands • Two probes will be used in this protocol 
 ◦ Cerebral perfusion: placed over the frontal cortex ◦ Lower-limb perfusion: placed over the muscle belly of the gastrocnemius
Example Set-up		
 • Researchers will follow manufacturer guidelines on appropriate probe placement • An opaque cloth (not shown) will be wrapped over the probe to prevent the influence of ambient light on infrared signals • For NIRS probe placement over the gastrocnemius: An 11L linear probe from the Logiq 6 ultrasound device will be used to ensure the NIRS device is not placed over a blood vessel. • The ultrasound device is only be used to ensure the probe is being placed only over the muscle belly of the gastrocnemius

Raw Data	 
 • Oxysoft, a proprietary software system developed by Artinis Medical Systems, will be used to collect and display raw data • Displayed are three signals each for total hemoglobin (greens), oxygenated hemoglobin (reds), and deoxygenated hemoglobin (blues)
Data Analysis	 
 • The NIRS devices emits three separate wavelengths to capture different depths of the • The spatially resolved signal working with the probe is capable of estimating absolute values for each variable used in this protocol
Data Reduction	 
 • A lab-designed macro will export the raw data to an Excel sheet • Column 1 represents the time point • A researcher will then select 30s sections for specific time points during the experimental conditions (e.g. immediately post-MAT, 5 minutes post-MAT)

[figure not shown]
[figure not shown]
Device 6: ActiGraph

Device		
 Company: ActiGraph Model: wGT3X-BT Location: Pensacola, FL
Example Set-up	  
SLEEP DIARY
 
Each line represents 24 hours from midnight one day to midnight the following day
 
Please enter on each line when you begin trying to sleep (BGN) and finish trying to sleep (FSH) for any sleep 10 minutes or longer. Also record if or when you take it off (OFF) and back on again (ON).
 
This line gives you an example on how to fill out the sleep log. Carry sleep time over to the next line if necessary.
 
Example: 000 020 040 060 080 1000 120 140 160 180 200 220 240 00:15 BGN 06:15 FSH 10:00-10:15 OFF 23:00 BGN
 
Date: / / 000 020 040 060 080 1000 120 140 160 180 200 220 240
 
Date: / / 000 020 040 060 080 1000 120 140 160 180 200 220 240
 
Date: / / 000 020 040 060 080 1000 120 140 160 180 200 220 240
 
Date: / / 000 020 040 060 080 1000 120 140 160 180 200 220 240
	
 Device is worn on the non-dominant wrist To maintain internal validity subjects will be asked to complete a sleep journal that details when the ActiGraph device is being worn, when the participant goes to sleep, and when he/she awakens. This information will only be used to validate the adherence of the participant to pre-test behaviors: Waking up at relatively the same time of the morning, no vigorous exercise 24hr prior

Raw Data		
 Upper image: 24 hour observation of counts of physical activity and ambient light throughout several days Lower image: More detailed view of physical activity counts.
Data Analysis		
 Trained researchers will use the returned sleep journal to set cut points for the beginning and end of sleep periods of the research participant This process allows more accurate reports of ambient physical activity before and during experimental sessions
Data Reduction		
 Data can be reduced on an hourly or daily basis Accelerometry data separates daily ambulation into different categories: sedentary, light, moderate, and vigorous

DEVICES 7 & 8: Data Acquisition (PowerLab) and Data Processing (LabChart)

Device		
 Company: ADInstruments Model: PowerLab 8/35 Location: Sydney, Australia Device will work in conjunction with LabChart software and NIBP cuff
--------	---	---

Example Set-up		
 Example set-up shown to an in the image to the left. Shown in this example: 
 Upper left: EKG Bottom PowerLab Unit: TCD inputs for eventual display on LabChart 																																																																																																																																																																																																																
Raw Data		
 Shown is LabChart receiving the signals interpreted by the PowerLab system 																																																																																																																																																																																																																
Data Analysis	
 LabChart 8 can perform real time or offline function, including data averaging, peak detection, derivates etc. 																																																																																																																																																																																																																	
Data Reduction	 
  
 	A	B	C	D	E	F	G	
 
 1	Heart Rate Mean beats/min	Mean Arterial mmHg	Systolic mmHg	SV mL	CO L/min	TPR mmHg/s/mL		
   
 2	51.6237	89.0879	62.3467	142.7481	107.1509	4.7202	5.8197	
 
 3	Mean	Mean	Mean	Mean	Mean	Mean		
 
 4	51.6237	89.0879	56.5191	120.0161	65.79	3.4163	3.3901	
 
 5	58.3777	108.4601	96.3322	152.8788	47.9453	2.8302	3.3908	
 
 6	62.4794	98.4316	44.0036	87.4436	47.9181	2.9075	4.2573	
 
 7	59.2781	80.0051	54.3536	131.3739	82.1288	4.9595	5.2451	
 
 8	51.6237	89.0879	62.3467	142.7481	107.1509	4.7202	5.8197	
 
 9								
 
 10								
 
 11								
 
 12								
 
 13								
 
 14								
 
 15								
 
 16								
 
 17								
 
 18								
 
 19								
 
 20								
 
 21								
 
 22								
 
 23								
 
 24								
 
 25								
  
		A	B	C	D	E	F	G	1	Heart Rate Mean beats/min	Mean Arterial mmHg	Systolic mmHg	SV mL	CO L/min	TPR mmHg/s/mL		2	51.6237	89.0879	62.3467	142.7481	107.1509	4.7202	5.8197	3	Mean	Mean	Mean	Mean	Mean	Mean		4	51.6237	89.0879	56.5191	120.0161	65.79	3.4163	3.3901	5	58.3777	108.4601	96.3322	152.8788	47.9453	2.8302	3.3908	6	62.4794	98.4316	44.0036	87.4436	47.9181	2.9075	4.2573	7	59.2781	80.0051	54.3536	131.3739	82.1288	4.9595	5.2451	8	51.6237	89.0879	62.3467	142.7481	107.1509	4.7202	5.8197	9								10								11								12								13								14								15								16								17								18								19								20								21								22								23								24								25								
 After the completion of a data collection set, summarized data is calculated by the software Data will be exported to lab Excel files for comparison amongst subjects and final analysis
	A	B	C	D	E	F	G																																																																																																																																																																																																											
1	Heart Rate Mean beats/min	Mean Arterial mmHg	Systolic mmHg	SV mL	CO L/min	TPR mmHg/s/mL																																																																																																																																																																																																												
2	51.6237	89.0879	62.3467	142.7481	107.1509	4.7202	5.8197																																																																																																																																																																																																											
3	Mean	Mean	Mean	Mean	Mean	Mean																																																																																																																																																																																																												
4	51.6237	89.0879	56.5191	120.0161	65.79	3.4163	3.3901																																																																																																																																																																																																											
5	58.3777	108.4601	96.3322	152.8788	47.9453	2.8302	3.3908																																																																																																																																																																																																											
6	62.4794	98.4316	44.0036	87.4436	47.9181	2.9075	4.2573																																																																																																																																																																																																											
7	59.2781	80.0051	54.3536	131.3739	82.1288	4.9595	5.2451																																																																																																																																																																																																											
8	51.6237	89.0879	62.3467	142.7481	107.1509	4.7202	5.8197																																																																																																																																																																																																											
9																																																																																																																																																																																																																		
10																																																																																																																																																																																																																		
11																																																																																																																																																																																																																		
12																																																																																																																																																																																																																		
13																																																																																																																																																																																																																		
14																																																																																																																																																																																																																		
15																																																																																																																																																																																																																		
16																																																																																																																																																																																																																		
17																																																																																																																																																																																																																		
18																																																																																																																																																																																																																		
19																																																																																																																																																																																																																		
20																																																																																																																																																																																																																		
21																																																																																																																																																																																																																		
22																																																																																																																																																																																																																		
23																																																																																																																																																																																																																		
24																																																																																																																																																																																																																		
25																																																																																																																																																																																																																		

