6 SAFETY MONITORING & MANAGEMENT

6.1 Adverse Event Risk

Investigators leading this project are knowledgeable of clinically healthy values for BP, cardiac output, and other experimental outcomes. It is anticipated the collection of values of clinical concern will be rare as those with a diagnosis of cardio-metabolic diseases will be excluded from this study entirely. However, in the event of clinically meaningful cardiovascular values, the participant will be notified of his or her results and consultation with faculty advisor, [name] will be completed on further action, if needed. It is ultimately the decision of the subject to follow through with action after gaining knowledge and receiving advice on his or her unfavorable cardiovascular health.

The devices used in this study are noninvasive. There are no known severely adverse events that have occurred with use of the stated devices.

VICORDER® - The system requires the placement of pressure cuffs over several arteries for the collection of PWV/A data. Pressure cuffs will only be inflated underneath a level of 65 mmHg. Physical harm or discomfort is unlikely and include, but are not limited to:

- Risk 1: Discomfort/unease: Infrequent (1 – 10%) – Application of a slight pressure over the carotid artery may impose a sense of unease for the participant. However, the light pressure used for this experimental protocol will in no way significantly damage cardiovascular structure or place the participant in danger. Investigators will make certain that communication on the procedures during testing session are clearly conveyed to the participant for comfort and safety.

Near-infrared spectroscopy (NIRS): Risk of injury or discomfort is extremely low due to this device. Possible physical harms are, but not limited to:

- Risk 1: Eye damage/irritation: Rare (<1%) – Please do not, at any point, stare into the light emitted from the NIRS probe
- Risk 2: Skin heating and irritation: Rare (<1%) – Wearing the NIRS probe for extended periods of time at once can theoretically lead to a warm feeling at the area where the probe is placed. However, this risk is minimal because the light emitted from this probe is not powerful enough to heat the skin. If you let the investigators know of any discomfort due to the probe, we will follow manufacturer guidelines to ensure the device is functioning correctly.

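### The VICORDER brachial cuff and the finger NIBP sensor share the non-dominant arm and run together, so each brachial inflation is upstream of the continuous pressure record

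*Combined protocol and SAP*

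**What the plan says.** The relevant instructions are spread over the device descriptions in section 3 and the schedules in sections 2.3 to 2.6.

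- **Brachial cuff.** Section 3, Device 1 (VICORDER): "Oscillometric pressure waveforms will be determined at the brachial artery of the non-dominant arm". The purpose given is to obtain brachial and central blood pressures.
- **Finger sensor.** Section 3, Device 3 (NIBP): "Wrist apparatus is strapped to the individual's non-dominant wrist", and "Device placed between distal and proximal inter-phalangeal joint of the index finger".
- **Recording.** For NIBP, "All measures collected from this device are continuously recorded during a testing session".
- **Epochs.** For NIBP, "Data reduction for this protocol will require the selection of 30s epochs at specific time points". The minutes are not listed, and Table 3 refers to a prearranged protocol that the plan does not reproduce. The TCD text asks that "selection of 30s epochs are synchronized amongst all measures and research participants to prevent bias". The NIBP text asks only that epochs be similar across measures. Times are named only as examples, under NIRS: "A researcher will then select 30s sections for specific time points during the experimental conditions (e.g. immediately post-MAT, 5 minutes post-MAT".
- **VICORDER times.** Section 2.3 and Table 2 put readings at 0, 5, 10, 15, 20 and 25 minutes after the MAT in both conditions. Table 3 says they are taken in triplicate.
- **Cuff pressure.** Device 1 describes inflation below systolic pressure. Section 6.1 adds: "Pressure cuffs will only be inflated underneath a level of 65 mmHg".

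Nothing in the text places the two devices on opposite arms, pauses NIBP during a VICORDER reading, or excludes inflation periods from the NIBP data.

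**The concern.** The finger sensor sits downstream of the brachial cuff on the same arm. Any effect of inflation on the limb can therefore enter the beat-to-beat pressure record, and that record is never interrupted. If the epochs are drawn at the VICORDER minutes, the values analysed would be those most exposed to the cuff and least representative of the undisturbed response to stress.

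Table 2 assigns baroreflex sensitivity, heart rate variability and heart rate to NIBP. NIBP is also the only continuous arterial pressure in the plan, and so the natural pressure input for static cerebral autoregulation, although the plan does not name that input. The synopsis says the study should help explain mechanisms, and these are the measures intended to do so. A disturbed stretch of beat-to-beat pressure cannot be recovered afterwards.

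**Working it through.** The plan states no figure to reproduce. The check compares limbs, then times, then epoch placement.

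**1. Limb.** The brachial reading is on the non-dominant arm (Device 1). The NIBP wrist unit is on the non-dominant wrist with its sensor on the index finger (Device 3). They share an arm, and the cuff is nearer the heart. The side of the brachial cuff for bfPWV is not stated separately. This does not matter here, because Table 2 gives central pressures, peripheral pressures and augmentation index the same minutes as bfPWV. A brachial reading is therefore due at every listed minute.

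**2. Time.** NIBP runs throughout. After the MAT there are 6 listed minutes with 3 readings each, so 6 × 3 = 18 VICORDER bfPWV readings per visit, the same in CON and SMS.

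**3. Epoch placement.** Let *t* be a listed VICORDER time, *c* the length of the reading and *e* the start of a 30 s epoch. The plan does not give *c*. Assume the reading starts at *t* and lasts 30 to 120 s.

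Overlap = max(0, min(*e* + 30, *t* + *c*) − max(*e*, *t*)) / 30

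- Epoch starts at *t*: (*t* + 30 − *t*)/30 = 30/30 = 100%.
- Epoch centred on *t*: (*t* + 15 − *t*)/30 = 15/30 = 50%.
- Epoch ends at *t*: 0/30 = 0%.

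The results are the same for every *c* in that range. The plan does not say which placement applies. At time 0 the third option is not open to a post-MAT epoch, because it would fall within the MAT. The timeline gives 0:00 to 1:00 to the VICORDER, so an epoch beginning at MAT completion lies wholly inside that slot, although brachial inflation need not fill it.

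**4. Is the tie between epochs and readings written down?** No. The two example times under NIRS (immediately and 5 minutes after the MAT) are both VICORDER times, and epochs are to be synchronised (TCD text) or similar (NIBP text) across measures. Together these make coincidence probable without stating it.

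**5. Room for a clean epoch.** Suppose each reading takes the one minute that the timeline allots at time 0 (an assumption for the later minutes). Then 300 − 60 = 240 s of each 5-minute interval is free, enough for 240/30 = 8 separate epochs.

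**6. Baseline.** In the CON timeline, sitting, continuous recording and the VICORDER window all begin at −15:00 and the MAT begins at −5:00. The window therefore covers 10 of 10 seated minutes. In SMS it covers 5 + 10 = 15 of 120 minutes, or 12.5%. Both shares are upper limits for brachial inflation, since these windows also hold cfPWV and faPWV readings and, in CON, ultrasound. Section 2.3 gives CON 20 minutes of sitting where the timeline shows 10, so the CON share is uncertain. The practical consequence is that an epoch rule based on time just before the first inflation might have nothing to sample in CON.

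**The case against.** The best reply is that the plan never ties an NIBP epoch to an inflation. The selection protocol is not reproduced, the named minutes are examples for another device, and the set-up and timing figures are not visible in the text reviewed. All of this stands. It limits the claim about epochs to a probability, but leaves the shared arm and simultaneous recording untouched.

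It is also fair to say that the affected outcomes are mechanistic, and that section 4.2 uses them to support discussion. A Lead II ECG is recorded alongside, so heart rate and heart rate variability need not depend on the finger signal.

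A reader might be tempted further, in ways the documents do not support:

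- **That the finger pulse is lost.** Table 2 wants systolic pressure from the VICORDER, which may suggest inflation above systolic. But the plan describes cuffs below systolic pressure and below 65 mmHg. Arterial occlusion is not what it sets out.
- **That a primary outcome is compromised.** The TCD analysis text times the R wave against a pressure waveform, and section 2.5 names NIBP as one such source. Yet brain PWV is listed under TCD, and dependence on the finger signal is not shown. bfPWV comes from the VICORDER itself.
- **That the two conditions are biased differently.** SMS has an additional early VICORDER set, but the last pre-stress window is −15 to −5 in both conditions and the post-MAT schedule is identical.
- **That the calf NIRS probe has the same problem.** The sides of the leg devices are not stated.

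**Conclusion.** The point holds as a set-up flaw of limited reach. The shared arm, the simultaneous recording and the lack of any safeguard are established from the text. Coincidence of the 30 s epochs with VICORDER readings is probable but inferred, and the possible overlap spans 0% to 100% according to a placement rule the plan does not give.

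That an upstream cuff can alter a finger-pressure signal is general measurement reasoning. The documents do not state it, and its size cannot be derived from them. The likely losses are baroreflex sensitivity and any NIBP pressure paired with TCD for static autoregulation. No effect on the primary or secondary comparisons has been shown. The case for acting rests on how easily the exposure can be removed, not on a demonstrated bias.

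**What to change.** In section 3, Device 1, change the VICORDER brachial cuff to the dominant arm, for bfPWV as well as for the pressures. Keep the finger NIBP on the non-dominant hand. Apply this at both visits, with path lengths taken on the side used, so that the within-person comparison stays like for like.

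As a backstop, add to the epoch protocol that NIBP epochs are chosen outside brachial-cuff inflation, at the same minutes in CON and SMS, and list those minutes. Word the rule as outside inflation, not as the 30 s before it, because CON may have no recorded time before its first reading. Do not delay the time-0 bfPWV reading to make room: it is a primary outcome, and the NIBP measures are not.

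The cost is a one-line set-up change and one sentence on epochs, with no new equipment, visits or participants. One dependency needs tidying. The dominant hand is needed for the Trails test, so the cuff must be finished with by then. The timeline allows this (VICORDER 25:00 to 30:00, cognitive tests from 30:00), but Table 2 lists both at 25 minutes and should be brought into line with the timeline.
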